The sample size is based on the expected between group difference in the WOOS end scores. The WOOS score 1 year after TSA surgery was 84.6 points in the Danish Shoulder Arthroplasty Registry in 2020 (7). The WOOS score after completing this exercise intervention in a feasibility study was 67 points (15). The assumed common SD was 27.1. The required power was set to 80%. Given a power of 0.80 to detect a difference between the two groups and using a two-sided significance level α =0.05, the estimated sample of each intervention group is 39 patients. Allowing for possible crossovers, loss-to follow-up and drop-outs the total number of patients in each group is 51 (1).

Framework

The overall objective of the trial is to determine whether surgical intervention results in a clinically and statistically significant greater improvement compared to exercise on WOOS, Disabilities of the Arm, Shoulder and Hand (DASH) (16), patient-reported pain intensity at rest, during activity, and nightly pain using the 100 mm VAS, the use of analgesics during the last week (paracetamol, NSAID, opioids) and adverse events. The primary hypothesis is that surgical intervention is superior to the exercise intervention at 12 months.

Blinded interpretation of the results

The blinded interpretation will be of the intention-to-treat analysis. The blinded analysis involves the primary outcome and key secondary outcomes. The principal investigator (JBL) will export data from REDCap and deliver the blinded dataset for analysis to the statistical analysist (AR). The senior statistician (EP) will supervise the analysis. The blinded results from the analysis of treatment A compared with treatment B will be presented to the project group followed by the development of the blinded interpretation. Interpretation version 1 assumes that group A had surgery, while interpretation 2 assumes that group A performed exercise. A draft of the blinded interpretation will be sent for approval by all co-authors. No other outcomes will be analyzed prior to an agreement of the blinded interpretation by all co-authors. All other analyses described in this document will be performed after the blinded interpretation is published (17).

Statistical interim analysis and stopping guidance

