A per protocol analysis will be conducted with patients in the surgical group undergoing surgery and for the exercise groups patients with a good adherence to the exercises are included. Poor adherence is defined as participating in less than 70% of the supervised exercise sessions. Another per protocol analysis will be of patients undergoing surgery regardless of randomization.

Lastly four as-treated analysis will be performed in which patients will be analyzed based on their adherence to the randomized treatment expecting four groups: (1) patients randomized to TSA and getting TSA, (2) patients randomized to exercise without undergoing TSA in the follow-up period, (3) patients randomized to exercise undergoing TSA in the follow-up period, (4) patients randomized to TSA not undergoing TSA in the follow-up period. One as treated analysis will be done on TSA patients versus good exercise adherence versus poor exercise adherence. And one as treated analysis on TSA patients randomized to TSA versus crossover TSA patients versus good exercise adherence versus poor exercise adherence.

SECTION 5: TRIAL POPULATION

Screening data

At all hospitals patients eligible for TSA will be screened for the inclusion and exclusion criteria. If they fulfil the criteria, they will be invited to participate. The number of patients who do not meet the criteria and the reason for ineligibility will be reported in a CONSORT flow chart (Figure 1).

Eligibility

Patients fulfilling the in- and exclusion criteria and are willing to participate are eligible for the PROACT trial. The inclusion criteria are:

Inclusion criteria:

- 1. Patients \geq 55 years
- Moderate to severe primary OA of the glenohumeral joint (Osteophyte larger than 3 mm, according to Samilson and Prieto (Samilson et al. 1983)
- 3. Eligible for surgery with standard TSA

Exclusion criteria:

- 1. Surgical need for bone graft or use of augmented glenoid component
- 2. Previous shoulder fracture (fracture of the proximal humerus or glenoid fracture)
- 3. Planned other upper extremity surgery within six months
- Rheumatoid arthritis or other types of arthritis not diagnosed as primary glenohumeral OA
- 5. Cancer diagnosis and actively receiving chemo-, immuno-, or radiotherapy
- 6. Neurological diseases affecting shoulder mobility (e.g., disability after previous stroke, multiple sclerosis, Parkinson's, Alzheimer's disease)

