	Baseline	Three months	One year	Baseline	Three months	One year	Adjusted
WOOS							
DASH							
Pain at rest							
Pain during							
activity							
Pain at night							
Use of							
analgesics*							
Adverse events*							
			Per-pr	otocol analy	ysis		
		TSA			Exercise		Improvement
							between the two
							groups
	Baseline	Three	One	Baseline	Three	One	Adjusted
		months	year		months	year	
WOOS							
DASH							
Pain at rest							
Pain during							
activity							
Pain at night							
Use of							
analgesics*							
Adverse events*							

Higher scores indicate desired (better) treatment outcome for WOOS. For the other outcomes lower scores indicate desired (better) treatment outcome.

*Analysed with risk difference, use of analgesics (yes/no), adverse events (yes/no).

	TS	Α		Ex	ercise		Cr	055-0V	er	No treatment		ıt	Improvements between the four groups	
	В	3M	1Y	В	3M	1Y	B	3M	1Y	В	3M	1Y	Adjusted	
WOOS														
DASH														
Pain at rest														
Pain during activity														
Pain at night														
Use of analgesics*														
Adverse events*														

Table 4: As treated analysis of the between group difference for the surgical group and exercise group in end-scores one year after intervention.

B=Baseline, 3M=Three months, 1Y=One year

Table 5: Usage of painkillers

		TSA group			Exercise gro	up
	Baseline	Three months	One year	Baseline	Three	One year
					months	
Use of painkillers, n (%) yes						
Type of painkillers, n (%)						
Paracetamol						
NSAID						
Morfin/opiods						
Other painkillers						
Usage of painkillers, n (%)						
Never						
Monthly						
Weekly						
Daily						

Table 6: Adverse and serious adverse events

	TSA group	Exercise group
Adverse events, n (%)		
Postoperative infections		
Instability		
Periprosthetic fracture		
Loosening		
Humeral component		
Glenoid component		
Both		
Injuries related to the exercise intervention		
Serious adverse events, n (%)		
Death		
Embolism		
Liver failure		
Renal failure		

*Serious adverse events resulting in the need for hospitalization or death in the first 4 weeks after surgery. Adverse events that occurred between baseline and 12 months follow-up but did not necessarily have a causal relationship between the treatments.

Table 7: Adherence to randomized treatment

	Exercise group
Training adherence	
Showed up for supervised sessions within the first three months of exercise, mean	
(SD)	

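### Tables 3 and 4 plan adjusted between-group contrasts on sets formed after randomisation, and no analysis of surgery received keeps the randomised comparison

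*SAP*

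**What the plan says.** Section 4 (Analysis populations) makes the intention-to-treat analysis primary, with patients kept in their allocated group whatever their adherence. It then adds:

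- **Per-protocol 1:** operated patients in the surgical arm, and exercise patients with good attendance. The cut is stated as "Poor adherence is defined as participating in less than 70% of the supervised exercise sessions".
- **Per-protocol 2:** all operated patients, whatever their allocation. No comparator is named.
- **As-treated 1:** "patients will be analyzed based on their adherence to the randomized treatment expecting four groups", the groups being allocation crossed with receipt of TSA.
- **As-treated 2:** TSA patients, good attenders and poor attenders.
- **As-treated 3:** patients operated as allocated, crossover TSA patients, good attenders and poor attenders.

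Table 3 places the per-protocol block below the intention-to-treat block with the same adjusted between-group column. The caption "Table 4: As treated analysis of the between group difference for the surgical group and exercise group in end-scores one year after intervention" heads a layout of four columns (TSA, exercise, crossover, no treatment), again with an adjusted comparison. Section 6 (Analysis methods) gives baseline score, sex, age and study site as the covariates of the primary model; none is named separately for these sets. Nothing marks the results as descriptive or non-randomised.

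**The concern.** Whether a patient attends, crosses over to surgery or declines it is decided after randomisation and may depend on how the shoulder is doing. If so, the groups differ in prognosis as well as in treatment. Covariates measured at baseline cannot correct for what happens afterwards.

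The SAP expects such departures. Crossover is one reason given for raising the sample size, and Section 4 predefines deviations in both directions. The effect of receiving surgery is therefore a natural question once the diluted intention-to-treat result is known. The plan answers it only with contrasts that randomisation no longer protects, set out in the same format as the protected one.

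**Working it through.** **1. What forms each set.** All five sets depend on receipt of surgery, crossover or attendance. Attendance enters per-protocol 1 and as-treated 2 and 3. It does not enter as-treated 1 or per-protocol 2.

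**2. The plan's own figure.** Inputs from Section 3, Sample Size:

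- surgery: "The WOOS score 1 year after TSA surgery was 84.6 points"
- exercise: "The WOOS score after completing this exercise intervention in a feasibility study was 67 points"
- SD: "The assumed common SD was 27.1"
- test: "using a two-sided significance level α =0.05"
- power: "The required power was set to 80" per cent

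The difference is 84.6 − 67 = 17.6. Then n = 2 × [27.1 × (1.960 + 0.842) / 17.6]² = 37.2, so 38 per group. The t-test version gives 38.2, so 39, as stated. The step to 51 implies a total allowance of 1 − 39/51 = 23.5%, not split between crossover and loss. Crossover and attendance rates below are therefore assumptions.

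**3. Shift from selecting good attenders.** Suppose attendance reflects a normal variable with correlation r to 12-month WOOS, and a share q attends well. The mean of the good attenders shifts by r × SD × φ(z)/q, where z is the cut point.

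- r = 0.3, q = 0.7: 0.3 × 27.1 × 0.348/0.7 = 4.0 points
- r = 0.2, q = 0.8: 0.2 × 27.1 × 0.280/0.8 = 1.9 points
- r = 0.4, q = 0.6: 0.4 × 27.1 × 0.386/0.6 = 7.0 points

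These are before covariate adjustment. If baseline correlates 0.5 with outcome, the residual SD is 27.1 × √0.75 = 23.5. The same values, now read as residual correlations, give 3.5 points (range 1.6 to 6.0).

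**4. The contrasts by simulation, adjusted for baseline.** There were 1,000,000 simulated patients per scenario. Assumptions: 20% crossover, 5% unoperated in the TSA arm, 75% good attenders, baseline-outcome correlation 0.5. Poor prognosis leads to crossover, and good prognosis to attendance and to declining surgery. True effect 17.6:

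| Contrast | Correlation 0 | 0.3 | 0.5 |
|---|---|---|---|
| Intention to treat | 13.3 | 13.2 | 13.2 |
| Per-protocol 1, attending crossovers kept | 14.2 | 11.0 | 9.1 |
| Per-protocol 1, attending crossovers removed | 17.7 | 12.4 | 9.3 |
| Operated as allocated v unoperated exercise | 17.7 | 14.8 | 12.9 |
| Any TSA v unoperated good attenders | 17.7 | 11.0 | 7.0 |

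There are two per-protocol rows because the SAP does not say whether good attenders who later have TSA stay in. With a true effect of zero, the same four adherence contrasts run from −2.8 to −6.7 at correlation 0.3 and from −4.7 to −10.6 at 0.5. At correlation 0 the selection bias vanishes, and keeping crossovers only dilutes the effect. The sign follows from the assumed pattern; the opposite pattern reverses it.

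**5. Precision of a complier-average estimate.** The intention-to-treat half-width at 51 per group is 1.96 × 27.1 × √(2/51) = 10.5. With 20% crossover and 5% unoperated, the arms differ in the share operated by 1 − 0.20 − 0.05 = 0.75, so the half-width is 10.5/0.75 = 14.0. Over 10% to 30% crossover and 5% to 10% unoperated it is 12.4 to 17.5.

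**6. Small cells in Table 4.** As a hypothetical case, 3 patients against 48 give 1.96 × 27.1 × √(1/3 + 1/48) = 31.6 points either side.

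**The case against.** The strongest reply is that nothing here is an error in the plan's main inference. The primary analysis is intention to treat, the blinded interpretation covers only that analysis, and the other analyses follow it. The SAP never claims that the per-protocol or as-treated results estimate the causal effect of surgery. All of that stands. What remains is that adjusted effects are still planned on these sets with no caveat.

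A complier-average analysis also has its own weakness here. It needs allocation to act on WOOS only through surgery received. Crossovers may be operated on later than patients allocated to surgery, leaving less recovery by 12 months. Unoperated TSA patients may get no trial exercise. If, as an assumption, 20% cross over and late surgery costs them 10 points, the estimate is inflated by 0.20 × 10/0.75 = 2.7 points, the same order as the bias it is meant to avoid. Nor does it address the effect of well-attended exercise. This stands, and it is why the analysis should be supportive and not the lead.

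A reader might infer three stronger points that the SAP does not support:

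- **A one-sided attendance filter runs through every adherence analysis.** The four-group analysis has none, per-protocol 2 names no comparator, and per-protocol 1 also filters the surgical arm, on having had the operation.
- **The planned contrasts favour exercise.** The SAP gives no relation between attendance or crossover and prognosis, and patients who feel well may also stop attending.
- **A complier-average analysis is shown to recover the true effect.** Multiplying 17.6 by 0.75 and dividing again is circular, and any simulation that builds in the method's assumptions will agree with it.

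**Conclusion.** The point holds for the supportive analyses only. All per-protocol and as-treated sets are defined by behaviour after randomisation, adjusted contrasts are planned on them beside the randomised one, and the stated covariates cannot remove selection arising during follow-up. No analysis of treatment received keeps the randomised comparison, although crossover is expected. The primary intention-to-treat result is unaffected.

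The size and direction of the bias cannot be known from the SAP. The shift of about 2 to 7 points in the mean of good attenders, before covariate adjustment, rests on assumed correlations of 0.2 to 0.4 and good attendance of 60% to 80%. Against a planned difference of 17.6, that could change how a supportive result is read. This is an inexpensive improvement worth making before analysis; it does not put the trial's conclusion in doubt.

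**What to change.** 1. Add a supportive, not lead, complier-average causal effect of TSA on 12-month WOOS in all randomised patients with 12-month data. Use two-stage least squares with allocation as instrument, TSA received before the 12-month assessment as treatment, and baseline WOOS, sex, age and site as covariates.
2. State its assumptions. Exclusion (allocation acts on WOOS only through surgery received) is doubtful for late crossovers and for unoperated TSA patients, so discuss it or test it in a sensitivity analysis. Monotonicity means that no patient would have TSA only if allocated to exercise.
3. Label all per-protocol and as-treated results as non-randomised. Report Table 4 and the attendance-based sets, including the per-protocol block of Table 3, descriptively, without adjusted contrasts presented as treatment effects.

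The cost is one model on data already scheduled in Table 1, plus changes to table layout and labels. The downside is a wider interval (half-width about 14 against 10.5 points for intention to treat, assuming 20% crossover and 5% unoperated) and reliance on assumptions that cannot be tested. Unlike the planned mixed model, the added analysis makes no use of 3-month scores from patients who lack a 12-month value.

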- 7. Other reasons for exclusion include mentally unable to participate or planned absence for more than 14 days in the first 3 months after baseline test
- 8. Unable to communicate in the respective languages of the participating countries.

Recruitment

The CONSORT flowchart will present the number of patients screened, excluded (with reasons), eligible for inclusion, randomized, receiving allocated treatment, withdrawals (with reasons), lost to follow-up (with reasons), included in the ITT analysis, included in the per protocol analysis.

Withdrawal/follow-up

Throughout the trial period the patients are allowed to withdraw from the study at any time. Patients who decide to withdraw will be encouraged to continue in the study as if they have received the intervention. Withdrawal will be classified into two options; (1) complete withdrawal from the study with no further follow-up and data-collection, (2) consent to follow-up assessments and data-collection. The number of withdrawals and the timing of withdrawal will be presented in the CONSORT flowchart (with reasons).

Baseline patient characteristics

Baseline characteristics will be presented as seen in Table 2. Categorical variables will be presented as numbers and percentages. Continuous variables will be presented as mean with

standard deviation (SD), if normally distributed and ad median with interquartile range (IQR) if not normally distributed. No tests of significance will be conducted for the baseline characteristics, imbalances of importance will be noted. Baseline and follow-up values for the primary and secondary outcomes will be presented as part of the analysis, as seen in Table 3.

SECTION 6: ANALYSIS

Outcome definitions

The Western Ontario Osteoarthritis of the Shoulder index score (WOOS)

The primary outcome will be presented as the between group difference on the 12-month follow-up score. WOOS is a valid and reliable patient-reported questionnaire assessing shoulder pain and function in a total raw score ranging from 0-1900, raw scores can be converted to a score from 0-100, where 0 indicates severe problems and 100 indicates no problems.

Key secondary outcomes

Disabilities of the Arm, Shoulder and Hand (DASH) (Lindenhovius et al. 2008); patientreported pain intensity at rest, during activity, and nightly pain using the 100 mm VAS; the use of analgesics during the last week (paracetamol, NSAID, opioids); serious adverse events and adverse events.

Analysis methods

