Descriptive statistics will be presented as means with standard deviation (SD) for all normally distributed continuous variables. Continuous variables that do not follow a normal distribution will be presented as median with interquartile ranges. Normal distribution will be determined by visual inspection of QQ-plots and histograms. Categorical outcomes will be presented as numbers with percentages.

The primary comparison in WOOS between groups will be conducted using a linear mixed model. Intervention group and time (3 months, 12 months) will be included as fixed effects and patient as random. Baseline score, sex, age and study site will also be included as fixed covariates. Interaction between study group and time will be included in the model to estimate treatment effect at each time point. 95% confidence intervals are estimated for each time point.

Due to the repeated mixed model analysis no missing data imputation will be conducted. A sensitivity analysis will be done using an analysis of covariance (ANCOVA) including baseline score, sex, age and study site as covariates with the same ITT approach for time (3 months and 12 months) separately.

Analysis for patient-reported DASH, pain intensity at 3 and 12 months will be analysed similar to the primary comparison. For binary variables (ie. the use of analgesics and adverse events) we use proportions to describe the number of events. For each binary outcome an unadjusted risk difference in proportions with 95% confidence interval of outcomes between study groups. Table 3 illustrates the primary analysis.

Response to treatment for the WOOS change score from baseline to 12 months and 3 months follow-up will be computed for each patient in both treatment groups. Response to treatment will be presented dichotomized (i.e. responder and non-responder) as number and percentage. The patients will be classified as a responder if they reach a minimal important change of 13.3 points or more from baseline to 12 months follow-up (19).

Missing data

As stated above, imputations will not be applied in this study due to the repeated mixed model analysis. Each randomized patient will be included in the intention-to-treat analysis with the collected data. In an attempt to collect data from all randomized patients, patients deciding to withdraw from the study, are still encouraged to attend the follow-up test.

Harms

Adverse and serious adverse events will be presented as number and percentage for each event.

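### Serious adverse events are a named key secondary outcome with no specified between-arm contrast, and the SAP does not say whether the adverse-event yes/no variable counts them

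*SAP*

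**What the plan says.** - **Outcome list (Section 6, Key secondary outcomes).** The safety item reads "serious adverse events and adverse events".
- **Analysis rule (Section 6, Analysis methods).** "For binary variables (ie. the use of analgesics and adverse events) we use proportions to describe the number of events". The next sentence gives the estimator: "For each binary outcome an unadjusted risk difference in proportions with 95% confidence interval of outcomes between study groups".
- **Harms (Section 6).** "Adverse and serious adverse events will be presented as number and percentage for each event". This is descriptive and names two classes.
- **Table 1.** Adverse events and serious adverse events have separate rows. Both are collected at 3 and 12 months.
- **Table 3.** Each panel (intention-to-treat and per-protocol) has one adverse-event row and no serious-event row. The footnote reads "Analysed with risk difference, use of analgesics (yes/no), adverse events (yes/no". Table 4 (as-treated) has the same single row.
- **Table 6.** The block headed "Serious adverse events, n" (%) holds death, embolism, liver failure and renal failure. These do not appear in the adverse-event block, which holds infection, instability, periprosthetic fracture, loosening and exercise injuries. The footnote gives each class its own description: "Serious adverse events resulting in the need for hospitalization or death in the first 4 weeks after surgery" and "Adverse events that occurred between baseline and 12 months follow-up but did not necessarily have a causal relationship between the treatments".

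**The concern.** The second key secondary objective is a comparison of safety between the arms. Section 3 also puts the key secondary outcomes through the blinded A-versus-B analysis, and no other outcome is analysed until its interpretation is agreed. A key secondary outcome that enters that step without a defined contrast leaves the analyst to choose one, or to omit it.

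The undefined adverse-event variable adds a second problem. Two competent analysts could code the Table 3 row differently. One could count any event. The other could count only events from the adverse-event block of Table 6. Because the listed serious events are described relative to surgery, the choice need not affect the two arms equally.

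**Working it through.** **1. Where each class appears**

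| Place in SAP | Adverse events | Serious adverse events |
|---|---|---|
| Section 2, safety objective | named | not named separately |
| Section 3, Framework | named | not named separately |
| Section 6, Key secondary outcomes | named | named |
| Section 6, binary-outcome rule | named | not named |
| Section 6, Harms | number and % | number and % |
| Table 1 | own row | own row |
| Table 3, both panels, and footnote | row, risk difference | no row |
| Table 4 | row | no row |
| Table 6 | own block | own block, no contrast column |

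The class named in the outcome list is therefore missing from every place that specifies a between-arm estimate. The per-protocol and as-treated tables repeat the same variable, so they do not fill the gap.

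**2. Time windows (Table 6 footnote)**

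Adverse events run from baseline to 12 months. Serious events are tied to the 4 weeks after surgery. An exercise patient who never has surgery has no such period. A serious-event risk difference built on that window would not compare like with like.

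**3. Size of the coding ambiguity**

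The SAP has no safety figure to reproduce. Its only relevant number is 51 patients per arm (Section 3, Sample Size). Let *a* and *b* be the numbers of patients with an event in the TSA and exercise arms:

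- RD = *a*/51 − *b*/51
- SE = √[*p*(1−*p*)/51 + *q*(1−*q*)/51], with *p* = *a*/51 and *q* = *b*/51
- 95% CI = RD ± 1.96 × SE (Wald)

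One more TSA patient counted as yes adds 1/51 = 0.0196, or 2.0 points.

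All event counts below are assumed, for illustration only.

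*Start A: 6 TSA and 3 exercise patients with a listed adverse event.*
- Serious-only patients not counted: 6/51 − 3/51 = 5.9 points; SE = 0.0559; CI −5.1 to 16.8.
- Three serious-only TSA patients counted: 9/51 − 3/51 = 11.8 points; SE = 0.0627; CI −0.5 to 24.1.

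*Start B: 5 in each arm.* Not counted, the RD is 0.0 (−11.5 to 11.5) however many there are. Counted:

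| Serious-only TSA patients | RD, points (95% CI) |
|---|---|
| 1 | 2.0 (−10.1 to 14.0) |
| 2 | 3.9 (−8.6 to 16.4) |
| 3 | 5.9 (−7.0 to 18.8) |
| 4 | 7.8 (−5.4 to 21.1) |

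The step per patient is the same from either start. All of these intervals include zero.

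**4. Interval method for a serious-event row**

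Take 4 serious-event patients against 0 (also assumed). The RD is 7.8 points. The Wald interval is 0.5 to 15.2, and the Newcombe score interval is −0.6 to 18.5. With counts this small, the choice of interval can decide whether zero is excluded, so it should be fixed in advance.

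**The case against.** A reader might infer that the plan scores patients with the gravest events as having no adverse event, and so makes surgery look safer. The documents do not support this, for four reasons.

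- No text makes the Table 6 blocks the definition of the Table 3 variable. Table 6 serves the Harms section.
- The Table 6 footnote describes adverse events broadly: baseline to 12 months, with no causal link needed. An embolism or death in that period fits the description.
- The safety objective and the Framework use adverse events alone for the whole safety comparison, which suggests an umbrella term.
- The estimator sentence applies to each binary outcome, and a serious adverse event (yes/no) can be read as one.

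Three further points are fair. Table 6 shows serious events by arm, so nothing is concealed. The differing schedules in Table 1 do not bear on the 12-month analysis, because the two rows diverge only from 2 years on. A footnote to Table 1 points to a description of adverse events that is not in the SAP text and may be in the protocol.

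These points defeat the stronger inference but do not close the gap. The sentence before the estimator introduces its list with *ie.*, which reads as complete, and the table shells follow that list. Elsewhere the SAP pairs the two terms as distinct classes. A definition held in the protocol could settle the coding, but it would not put a serious-event contrast into this plan's analysis rule or tables.

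**Conclusion.** The point holds as an inconsistency and a gap in specification. A named key secondary outcome has no specified between-arm contrast, and the adverse-event variable that does have one is not defined as including or excluding serious events. It does not show that serious events are omitted from reporting, or that the safety result will be biased.

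The only firm figure is the step of 2.0 points per TSA patient whose only event is serious. It assumes 51 analysed per arm and applies only if the narrow reading is used. How many such patients there will be cannot be derived from the SAP, so the total shift is unknown. The primary outcome is unaffected. The change should be made before the blinded analysis.

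**What to change.** 1. In Section 6, Analysis methods, and in the footnotes to Tables 3 and 4, define the adverse-event variable as at least one adverse event, serious or not, from baseline to 12 months.
2. Add a row for serious adverse events (yes/no), with its own risk difference and 95% CI. Name the interval method, preferably score or exact because events will be few. Name serious events in the binary-outcome rule and in the Framework, so that the same two outcomes appear throughout.
3. Reconcile the serious-event window in the Table 6 footnote so that one analysis window applies to both arms, including exercise patients who never have surgery.

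**Cost.** SAP wording and one extra row, whose interval will be wide. Table 1 already schedules serious events at 3 and 12 months, so no new assessment is needed. The third item takes more than a wording edit if serious events in unoperated patients have so far been recorded only against a surgery date. The trial team should check that before the data are unblinded.

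### The primary mixed model states no visit-specific variance, so as ordinarily read the 12-month WOOS standard error, confidence interval and p-value pool the 3-month and 12-month residual variances

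*SAP*

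**What the plan says.** SAP Section 6 (Outcome definitions) fixes the primary contrast: "The primary outcome will be presented as the between group difference on the 12-month follow-up score". Under Analysis methods in the same section, the model for it is a linear mixed model: "Intervention group and time (3 months, 12 months) will be included as fixed effects and patient as random". The adjustment set follows: "Baseline score, sex, age and study site will also be included as fixed covariates". A group-by-time interaction gives a treatment effect at each visit, and "95% confidence intervals are estimated for each time point".

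No residual covariance structure, visit-specific variance, robust standard error or degrees-of-freedom method is stated. The software section names R but no package or function. The model is later given a label, "Due to the repeated mixed model analysis no missing data imputation will be conducted", but the word repeated does not name a structure.

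Two further statements bear on the point. A per-visit check is planned: "A sensitivity analysis will be done using an analysis of covariance (ANCOVA) including baseline score, sex, age and study site as covariates", run for each time point separately. The primary model is also reused: "Analysis for patient-reported DASH, pain intensity at 3 and 12 months will be analysed similar to the primary comparison".

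**The concern.** A random intercept with a single residual variance gives every follow-up score the same total variance. The group-by-time interaction frees the mean difference at each visit but leaves the variance common to both. The 12-month standard error is therefore built partly from the scatter of 3-month scores, which are not part of the primary outcome.

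If adjusted scores vary more at 12 months than at 3 months (r < 1), the 12-month interval is too narrow and the type I error exceeds 5%. If they vary less (r > 1), the test is conservative and loses power. The SAP ties its p < 0.05 criterion to the primary outcome, so this is the result on which the main conclusion turns. Imputation is ruled out because of this model, so its covariance also governs how 3-month scores inform the 12-month estimate when 12-month scores are missing.

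**Working it through.** **Inputs from the SAP (Section 3, Sample Size; Section 4).** Expected WOOS 84.6 and 67, difference 17.6; "The assumed common SD was 27.1"; two-sided alpha 0.05; power 80%; 39 per group, raised to 51 to allow for crossover, loss and drop-out. The SD is a single planning value, not split by visit.

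**The plan's own figure.** With difference 17.6 and SD 27.1, the normal approximation gives 38 per group. The t-based calculation gives 39 (power 0.798 at 38, 0.808 at 39). The stated 39 reproduces.

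**Assumed.** r is not in the SAP, so a range is shown. It is the ratio of residual SDs (3-month over 12-month) after adjustment for baseline score, sex, age and site.

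**Complete data.** The model uses the mean of the two visit variances, so reported SE / correct SE at 12 months is k = sqrt((1 + r²)/2). Type I error = 2(1 - Phi(1.96k)). Power for a test with nominal 80% = 1 - Phi(1.96k - 2.80).

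| r | k | SE error | Type I error | Power (nominal 80%) |
|---|---|---|---|---|
| 0.8 | 0.906 | -9% | 7.6% | not a valid gain |
| 0.9 | 0.951 | -5% | 6.2% | not a valid gain |
| 1.0 | 1.000 | 0 | 5.0% | 80% |
| 1.1 | 1.051 | +5% | 3.9% | 77% |
| 1.25 | 1.132 | +13% | 2.7% | 72% |

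**Confidence interval half-width at 39 per arm.** The formula is 1.96 x 27.1 x sqrt(1 - c²) x sqrt(2/39) x k, with c an assumed baseline correlation.

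| c | Correct (k = 1) | Reported, r = 0.8 | Reported, r = 1.25 |
|---|---|---|---|
| 0 | 12.0 | 10.9 | 13.6 |
| 0.4 | 11.0 | 10.0 | 12.5 |
| 0.6 | 9.6 | 8.7 | 10.9 |

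**Missing 12-month scores.** Treating the whole allowance as loss gives 1 - 39/51 = 23.5%, taken as missing completely at random. The large-sample limit of the random-intercept fit tilts the pooled variance towards 3 months. At between-visit correlation 0.6, k = 0.890, 0.943, 1.000, 1.059, 1.151 for the same five values of r. Across correlations 0.4 to 0.8 the type I error is 8.1 to 8.2%, 6.4 to 6.5%, 5.0%, 3.8% and 2.4%.

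**Equal raw SDs do not guarantee r = 1.** Take raw variance 1 at both visits and assumed baseline correlations of 0.6 at 3 months and 0.3 at 12 months. The model has one baseline slope, (0.6 + 0.3)/2 = 0.45. The residual variances are 1 - 2(0.45)(0.6) + 0.45² = 0.6625 and 1 - 2(0.45)(0.3) + 0.45² = 0.9325. So r = sqrt(0.6625/0.9325) = 0.84 and the type I error is 7.0% (simulated 6.4%, Monte Carlo SE 0.4 points). Reversing the correlations gives r = 1.19 and 3.2%.

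**Simulation.** Settings: 51 per arm, seven equal sites, all planned fixed effects, REML, between-visit residual correlation 0.6, no true effect, 4000 runs per cell, Monte Carlo SE 0.25 to 0.42 points. Rejection rates for the random-intercept model:

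| r | Complete data | 23.5% missing at 12 months |
|---|---|---|
| 0.8 | 7.6% | 7.4% |
| 0.9 | 6.4% | 6.9% |
| 1.0 | 4.6% | 4.6% |
| 1.1 | 3.5% | 3.4% |
| 1.25 | 2.6% | 3.0% |

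In the same data an unstructured 2x2 covariance gave 4.4 to 5.7% and the separate 12-month ANCOVA 4.4 to 5.5%. Differences of a few tenths between cells mean nothing.

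**The case against.** The case against is that no error has been shown. A mixed model with a random patient term is a standard, coherent choice for two visits, and the SAP never says that the residual variance is homogeneous. Every value of r above is assumed, and for r between 0.9 and 1.1 the type I error stays between 3.9% and 6.2%. A separate 12-month ANCOVA is already planned and would expose a material discrepancy.

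The detailed figures can also be challenged:

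- The 23.5% loss is an upper-end use of the allowance, because the allowance also covers crossovers, who stay in the intention-to-treat analysis.
- The 72% power figure starts from exactly 80%. With the SAP's 17.6 and 27.1, r = 1.25 and complete data, power at 39 per arm is 74%, 82% and 91% for c = 0, 0.4 and 0.6. At 51 per arm it is 86%, 91% and 97%.

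These points stand as limits on the size. They do not remove the problem. The SAP supports r = 1 no better than any other value. If another structure was intended, it has to be written down, since two analysts could otherwise obtain different p-values from the same data. The ANCOVA is a sensitivity analysis: if it disagreed with the mixed model, the primary result would still be the one with the pooled variance.

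**Conclusion.** The point holds, as a weakness in how the primary model is specified. With patient as the only random term and no visit-specific variance, validity of the 12-month test and interval depends on equal adjusted residual variances at 3 and 12 months, which the SAP neither states nor supports. The consequence is nil at r = 1, modest for r near 1, and reaches a type I error of about 7.6 to 8.2% at r = 0.8 or 2.4 to 2.7% at r = 1.25. These figures rest on the ordinary random-intercept reading, on the assumed range of r and, at their outer ends, on 23.5% of 12-month scores being missing completely at random. Which direction applies cannot be told from the SAP. It should be fixed before the analysis because the remedy is almost free.

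**What to change.** State the covariance in SAP Section 6, Analysis methods. Suggested text:

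> *The 3- and 12-month scores within a patient will be modelled with an unstructured 2x2 covariance matrix fitted by REML. The group contrast at 12 months is the primary estimate.*

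This matrix replaces the random patient intercept. Keep the stated fixed effects, and keep the separate 12-month ANCOVA as the sensitivity analysis. Name the degrees-of-freedom method in the same place, so that the p-value is fully determined. Use the same model for DASH and the three pain scales.

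The cost is a sentence or two and a small change in code, with three covariance parameters instead of two. In simulation at r = 1 the mean standard error, in units of the 12-month residual SD, was 0.2006 against 0.2007 with complete data and 0.2197 against 0.2199 with 23.5% missing, so no loss of precision was visible. No new data are needed and the estimand is unchanged.
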